6. STUDY ASSESSMENTS

6.1. Informed Consent

Prior to conducting any protocol-specific procedures for Phase 1b and Phase 2, written informed consent and any other authorizations must be signed and dated by the subject or subject's legal representative ([Section 12.4](#)).

6.2. Tumor Molecular Alteration

Perform molecular testing as per [Section 4.1](#) and the Schedule of Activities ([Table 1](#)).

Molecular testing to determine eligibility can be performed in advance with no time limit (e.g., the subject can be tested while being treated on another anticancer therapy).

Source documents (molecular pathology report detailing the specific test that confirms KRAS mutational status) should be submitted for the Sponsor's approval of eligibility.

Adequate archival tissue should be available for shipment to the Sponsor's designated central laboratory. A fresh biopsy is required if no adequate previously taken and stored tumor sample is not available.

6.3. Tumor Treatment History

All prior therapies, including duration and best response of targeted therapies, prior chemotherapy, and/or immunotherapy regimens and will be recorded in the applicable eCRF. If brain metastases are present, prior radiation and methods of radiation (e.g., whole brain radiation, stereotactic radiosurgery) should also be recorded.

6.4. Demographics

Demographic information (e.g., date or year of birth and race) will be recorded at Screening, as allowed per local country privacy law regulations.

6.5. Medical History

Relevant medical history, including history of current disease, other pertinent clinical conditions, and information regarding underlying disease will be recorded at Screening.

6.6. Physical Examination

A complete physical examination, including neurological examination will be performed by either the Investigator or a sub-Investigator according to the Schedule of Activities ([Table 1](#)).

The neurological examination will include assessments of the following symptoms: dizziness, dysgeusia, paresthesia, ataxia, headache, neuralgia, extrapyramidal disorder, memory impairment, concentration impairment, somnolence, and cognitive disturbance.

Height and weight will be collected as part of the physical exam. Height will be collected at Screening only.

Clinically significant abnormal findings must be recorded in the applicable eCRF and followed by the Investigator, sub-Investigator, or other qualified site staff at the next scheduled visit or earlier as clinically indicated.

6.7. Ophthalmologic Examination

All subjects must undergo a baseline, standard ophthalmologic exam at Screening. The exam will include direct and indirect fundoscopic exams, visual acuity (corrected), visual field examination, and tonometry, with special attention to any retinal abnormalities that are predisposing factors for RVO or CSR. After Screening, additional ophthalmologic exams will be performed only as symptomatically warranted.

6.8. Performance Status

The ECOG performance status will be assessed at Screening and according to the Schedule of Activities ([Table 1](#)).

6.9. Vital Signs

Body temperature, blood pressure, heart rate, and respiratory rate will be performed at timepoints outlined in the Schedule of Activities ([Table 1](#)).

6.10. Subject Diary and Compliance

All doses of study drugs (i.e., repotrectinib and trametinib) and dosing diaries will be dispensed by the appropriately designated study staff at the investigational site.

Subjects will be required to bring the dosing diary and all empty and partially used study drug bottles and any leftover study drug to every visit. The number of capsules and/or tablets returned by the subject will be counted, documented, and recorded. Treatment compliance will be evaluated by noting the discrepancy among the assigned dose, the dose administered, and the reason for the discrepancy will be recorded in the source documents.

6.11. Laboratory Assessments

Laboratory assessments as described in [Table 7](#) below will be performed per the Schedule of Activities ([Table 1](#)).

Table 7: Safety Laboratory Tests

Hematology	Complete blood count with differential: hemoglobin, platelets, WBC, absolute neutrophils, absolute lymphocytes, absolute monocytes, absolute eosinophils, absolute basophils
Chemistry	ALT, AST, ALP, sodium, potassium, magnesium, chloride, total calcium, total bilirubin, BUN or urea, creatinine, uric acid, glucose (nonfasted), lipid panel (total cholesterol, LDL, HDL, triglycerides), albumin, phosphorus or phosphate, bicarbonate, total protein, lactate dehydrogenase, amylase, lipase
Coagulation	PT or INR, PTT
Urinalysis	Urine dipstick for urine protein: If positive and clinically significant, microscopic (Reflex Testing) Urinalysis includes the analysis of protein, glucose, ketones, blood, and specific gravity. A microscopic (white blood cells/high-power field [HPF], red blood cells/HPF, and any additional findings) exam need be performed only if the urinalysis result is abnormal.
Pregnancy Test	Serum pregnancy test for female subjects of childbearing potential (Section 6.12)

Abbreviations: ALP = alkaline phosphatase; ALT = alanine aminotransferase; AST = aspartate aminotransferase; BUN = blood urea nitrogen; HDL = high-density lipoprotein; INR = International normalized ratio; LDL = low-density lipoprotein; PT = prothrombin time; PTT = partial thromboplastin time; WBC = white blood cell.

Note: For potential Hy's Law cases, in addition to repeating AST and ALT, laboratory tests should include albumin, creatine kinase, total bilirubin, direct and indirect bilirubin, gamma-glutamyl transferase, prothrombin time (PT)/INR, alkaline phosphatase, total bile acids and acetaminophen drug and/or protein adduct levels.

6.12. Pregnancy Test

For female subjects of childbearing potential, a serum pregnancy test, with sensitivity of at least 25 mIU/mL, will be performed as per the Schedule of Activities ([Table 1](#)). Only subjects with negative serum pregnancy test results can enroll in the study.

Following a negative pregnancy test result at Screening, appropriate contraception must be commenced, and another negative pregnancy test result will then be required at the baseline visit before a subject may receive study drug. Additional pregnancy tests may also be undertaken if requested by Institutional Review Boards/Ethics Committees or if required by local regulations. In case of a confirmed pregnancy, the subject will be withdrawn from study drug but may remain in the study.

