- Dosing Diary:** On Day 1 of each cycle, a new dosing diary will be provided to the subject. All subjects are required to complete dosing diary daily in conjunction with administration of repotrectinib and trametinib. At C1D1 all subjects should be trained by the site personnel how to complete the diary and inform them that all efforts should be made to record the dosing information as accurate as possible. The diary needs to be returned to the clinic together with the remaining study drug at each study visit. Study drug compliance and accountability needs to be reviewed at each study visit by the site personnel.
- Complete Blood Count with Differential:** White blood cell count, hemoglobin, platelets, absolute neutrophils, absolute lymphocytes, absolute monocytes, absolute eosinophils, and absolute basophils. On on-site dosing days, assessments will be performed **before** the dose of study drug is given. Complete Blood Count with Differential is *optional* on C1D1 if performed within the past 7 days.

11. **Complete Chemistry Panel:** ALT, AST, ALP, sodium, potassium, magnesium, chloride, total calcium, total bilirubin, BUN or urea, creatinine, uric acid, glucose (nonfasted), lipid panel (total cholesterol, LDL, HDL, triglycerides), albumin, phosphorus or phosphate, bicarbonate, total protein, lactate dehydrogenase, amylase, lipase. On on-site dosing days, assessments will be performed **before** the dose of study drug is given. Complete Chemistry Panel is *optional* on C1D1 if performed within the past 7 days.

12. **Coagulation:** Prothrombin time/international normalized ratio, partial thromboplastin time. On on-site dosing days, assessments will be performed **before** the dose of study drug is given. *Optional* on C1D1 if performed within the past 7 days.

13. **Serum Pregnancy Test:** For female subjects of childbearing potential, a serum pregnancy test, with sensitivity of at least 25 mIU/mL, will be performed during Screening, Cycle 1 Day 1 (*optional* if performed within the past 7 days.), Cycle 2 Day 1 and Day 1 of each subsequent cycle, EOT, and Safety Follow-up visit. Only subjects with negative serum pregnancy tests can enroll. If the results of the serum pregnancy test are not available during the clinic visits (e.g., C2D1, C3D1, C4D1, etc.), a urine pregnancy test may be performed.

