When coinciding with blood sample draws for PK, the ECG assessment should be performed prior to blood sample collection such that the blood sample is collected at the nominal time. ECGs performed within 10% of the nominal time (e.g., within 6 minutes of the 60-minute assessment) from dosing are acceptable. In addition to these timepoints, ECGs should be repeated as clinically indicated. Additional ECG timepoints may be included based on the emerging data. Interpretation of the tracing will be made by a central ECG laboratory. Each ECG tracing should be labeled with the study number, subject initials, subject number, and date, and kept in the source documents at the study site. Only clinically significant abnormalities will be recorded in the AE CRF page. Clinically significant abnormalities at Screening/baseline should be recorded on the relevant medical history/current medical conditions CRF page. Clinically significant findings must be discussed with the Sponsor's Medical Monitor before enrolling the subject in the study.

17. **Echocardiography or MUGA for LVEF Assessments:** Echocardiography to be performed at Screening, on Cycle 2 Day 1 (\pm 7 days), and after every three cycles of treatment (\pm 7 days) (Cycles 4, 7, 10, 13, and so on), and at the Safety Follow-Up visit (\pm 7 days).

18. **Pharmacokinetic Blood Sampling:** All measurement times are relative to combination dose of repotrectinib and trametinib unless otherwise specified. Samples obtained within 10% of the nominal time (e.g., within 6 minutes of the 60-minute sample) from dosing will not be considered as a protocol deviation, as long as the exact time of the sample collection is noted on the source document and data collection tool (e.g., CRF/DCT). Blood samples will be collected on the following days:

- a) Day 1: at pre-dose (0 hour), at 1, 2, 4, 6, 8, and 24 hours post-dose
- b) Cycle 1 Day 8: at pre-dose (0 hour), and 2 hours post-dose
- c) Cycle 1 Day 15: at pre-dose (0 hour)
- d) Cycle 1 Day 22: at pre-dose (0 hour), at 1, 2, 4, 6, 8, and 24 hours post-dose
- e) Cycles 2-6, Day 1: at pre-dose (0 hour), and 2 hours post-dose
- f) At End of Treatment

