21. **Bone Scans:** Bone scans (or bone MRI if preferred by Investigator) will be performed at baseline (28 days prior to Cycle 1 Day 1) if bone metastases are suspected. In addition, bone scans can be performed if clinically indicated per Investigator's discretion. These scans are only repeated for subjects having a baseline scan, to confirm the absence of bone metastases in case of a Complete Response (CR). Subject responses will be confirmed \geq 4 weeks later after the initial documentation of response by the Investigator.

22. **Adverse Events:** All AEs, whether reported by the subject or noted by study personnel, will be recorded in the subject's medical record and on the Adverse Event CRF at each subject contact. After informed consent for the clinical trial has been obtained but prior to initiation of study drug, only SAEs related to protocol-mandated assessments should be reported. After initiation of study drug, all AEs, regardless of relationship to study drug, will be reported until at least 28 days after the last dose of study treatment. Any SAEs occurring any time after the reporting period must be promptly reported if a causal relationship to the study drug is suspected.

23. **Concomitant Medications and Non-Drug Supportive Interventions:** All concomitant medications and non-drug supportive interventions should be recorded in the CRF.

24. **Survival Follow-Up:** For subjects discontinuing the study treatment due to documented radiographic progression, obtain survival status via phone call or medical chart review, including information about subsequent anticancer therapies (including best response) every 3 months until death, loss of follow-up, or withdrawal of consent, whichever comes first. For subjects discontinuing the study treatment prior to documented radiographic progression, tumor assessments should continue on the schedule approximately every 2 months or at the current scan interval at the time of treatment discontinuation until radiographic evidence of disease progression, the start of a subsequent anticancer therapy, or decision to no longer treat (e.g., supportive care only), whichever is first.

TABLE OF CONTENTS

TURNING POINT THERAPEUTICS APPROVAL	2
PRINCIPAL INVESTIGATOR STATEMENT OF AGREEMENT	3
PROTOCOL SYNOPSIS	4
SCHEDULE OF ACTIVITIES.....	15
ABBREVIATIONS AND DEFINITION OF TERMS.....	27
1. INTRODUCTION	32
1.1. Repotrectinib Mechanism of Action and Indication.....	32
1.2. Background.....	32

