7. STUDY CONDUCT

Scheduled protocol-related activities will be performed at specified timepoints and within windows as outlined in the Schedule of Activities ([Table 1](#)). If a visit is missed for any reason, the next scheduled visit should occur as originally planned.

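### Footnote 13 of Table 1 allows a woman tested once in the 7 days before Cycle 1 Day 1 to be dosed without the second negative pregnancy test that Section 6.12 requires

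*Combined protocol and SAP*

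**What the plan says.** Section 6.12 sets the rule for women of childbearing potential. Its first paragraph refers timing to the schedule: "a serum pregnancy test, with sensitivity of at least 25 mIU/mL, will be performed as per the Schedule of Activities". Its second paragraph adds a condition for dosing. After a negative Screening result contraception is started, and then "another negative pregnancy test result will then be required at the baseline visit before a subject may receive study drug". No exception is attached.

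Footnote 13 of Table 1 lists the testing times: Screening, Cycle 1 Day 1, Day 1 of each later cycle, End of Treatment and Safety Follow-up. The Cycle 1 Day 1 test is marked as optional "if performed within the past 7 days.), Cycle 2 Day 1 and Day 1 of each subsequent cycle". The same footnote provides a fallback for later visits: if serum results "are not available during the clinic visits (e.g., C2D1, C3D1, C4D1, etc.), a urine pregnancy test may be performed".

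Three other places bear on the point. Section 7.2 sends in-clinic dosing visits to the pre-dose list in Section 7.2.1, which includes blood for a pregnancy test and carries no 7-day waiver; Table 1 shows Cycle 1 Day 1 as an in-clinic dosing day. Section 7 states the general rule: "Scheduled protocol-related activities will be performed at specified timepoints and within windows as outlined in the Schedule of Activities". Inclusion criterion 9 asks for one negative serum test during screening.

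**The concern.** Section 6.12 makes a second negative result a condition for receiving study drug. Footnote 13 can remove that second test, and nothing in it says that the test which triggers the waiver must be additional to the Screening test. For some women the same conduct therefore complies with Table 1 and departs from Section 6.12.

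What is at stake is embryo-fetal exposure to two study drugs. A repeat test just before dosing is there to catch a pregnancy that the first test missed or that began after it. The protocol treats such exposure seriously: Section 6.12 withdraws a woman with a confirmed pregnancy from study drug, and Section 8.3 requires pregnancies to be reported within 24 hours.

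**Working it through.** There is no sample size, power or error rate to reproduce. The check compares the texts and counts days.

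**Inputs**
- Section 6.12: one negative test at Screening plus another at the baseline visit, so 1 + 1 = 2 before the first dose.
- Footnote 13: a Screening test, plus a Cycle 1 Day 1 test unless one was done in the previous 7 days.
- Table 1 heading and footnote 1: Screening lasts up to 28 days from consent, with no minimum length. The only Screening test can therefore fall in the last week.
- Table 1: 28-day cycles, and a window of ± 2 days at Cycle 2 Day 1.

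**Step 1. Negative tests needed before the first dose, by day of the single Screening test**

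| Day of Screening test | Section 6.12 | Footnote 13 | Result |
|---|---|---|---|
| Day -28 to Day -8 | 2 | 2 (Cycle 1 Day 1 test not waived) | agree |
| Day -7 to Day -1 | 2 | 1 (Cycle 1 Day 1 test waived) | conflict |

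**Step 2. When the next scheduled test falls if the waiver is used.** Cycle 2 Day 1 is Day 28 + 1 = 29, so with its window it runs from Day 29 - 2 = 27 to Day 29 + 2 = 31.
- Days since first dose (Day 1): 27 - 1 = 26 to 31 - 1 = 30.
- Days since her only test, with no Day 0: a Day -1 test is 1 day before the first dose, giving 26 + 1 = 27 at the least; a Day -7 test is 7 days before it, giving 30 + 7 = 37 at the most.

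**Step 3. Can the texts be met together?** Yes. The footnote makes the Cycle 1 Day 1 test optional and does not forbid it. Doing the test that day satisfies Section 6.12, Section 7.2.1 and Table 1. The fault is that the footnote permits an omission that Section 6.12 does not.

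**A separate, smaller mismatch.** Inclusion criterion 9 gives a closed list of highly effective contraceptive methods: sterilization, IUD, IUS, injectables and implants. Section 7.8.5 also accepts established combined hormonal methods given intravaginally or transdermally. A woman using a ring or patch is covered by one list and not by the other.

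**The case against.** The best defence is that Section 6.12 itself sends timing to Table 1, so the footnote governs. The waiver also looks deliberate: the same 7-day allowance is given for blood count, chemistry, coagulation and urinalysis in footnotes 10, 11, 12 and 14. On that view the protocol simply accepts one recent negative test, and inclusion criterion 9, which asks for only one, agrees.

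Part of this stands. The waiver may well be intended, and eligibility is not in conflict, since both Section 6.12 and footnote 13 require a negative serum result to enrol. But the deferral sits in the first paragraph of Section 6.12, and the second paragraph then adds its own condition for dosing. If the footnote overrides that condition, the words calling for another result have no effect for these women. The other laboratory tests have no comparable dosing condition in their own section. Section 7.2.1 also points towards testing, though only as support: it is a general list, and it also names a cfDNA sample that Table 1 does not schedule on Cycle 1 Day 1.

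A reader might infer more than the documents support:
- *That sites will follow the footnote, or have no answer.* Sections 7 and 6.12 point to Table 1, but Section 7.2.1 points the other way, and testing on Cycle 1 Day 1 meets every section. Nothing predicts what sites will do.
- *That the conflict turns on an undefined baseline visit.* Footnote 21, for instance, uses baseline for the screening period. Section 6.12, however, separates Screening from the baseline visit in one sentence, and Cycle 1 Day 1 is the natural reading. One test cannot be another test on either reading.
- *That the contraceptive lists also conflict over a vasectomized partner or over men.* Inclusion criterion 9 lists prior sterilization for women who, by its own definition, are not themselves sterilized, so a sterilized partner is arguably covered. Its requirement for men binds every male subject whether or not Section 7.8.5 repeats it.

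**Conclusion.** The inconsistency is real, sits in the current text, and is minor. It affects women of childbearing potential whose only Screening test falls on Day -7 to Day -1. For them footnote 13 permits one test before the first dose where Section 6.12 requires two, and the next scheduled test comes 26 to 30 days after dosing starts. Unscheduled tests remain possible, because Section 6.12 allows extra ones at the request of an ethics committee or under local regulations.

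The documents do not say how many women this would be, or how many pregnancies the repeat test would detect, so no risk can be put on it. Inclusion criterion 9 starts contraception at screening, so a last-week test may already follow its start; what is lost is the repeat test. The ORR analysis, the DLT assessment, the sample size and the error rates are untouched.

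**What to change.** 1. In footnote 13 of Table 1, delete the 7-day waiver for the Cycle 1 Day 1 pregnancy test.
2. In Section 6.12, state that the baseline visit is Cycle 1 Day 1 pre-dose and that a negative result is needed before the first dose.
3. Extend footnote 13's urine-test allowance, whose examples begin at Cycle 2 Day 1, to Cycle 1 Day 1 for when the serum result is not back. This is part of the amendment; without it, dosing would wait for the serum result.
4. Separately, use one contraceptive list in inclusion criterion 9 and Section 7.8.5, saying whether combined intravaginal and transdermal methods are accepted.

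Rewording Section 6.12 to accept one test within 7 days would also end the conflict, but it gives up the second test. That choice is a safety judgement, since the documents give no estimate of what the second test adds.

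The cost is one extra pregnancy test for each affected woman. Blood is already drawn before dosing at that visit, because PK sampling in footnote 18 is specified as "Day 1: at pre-dose (0 hour), at 1, 2, 4, 6, 8, and 24 hours post-dose". The rest is protocol wording.

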6.13. Cardiac Safety Monitoring

6.13.1. Electrocardiogram

Triple lead (with a 10-second rhythm strip) tracings will be used for all ECGs. It is preferable that the machine used has a capacity to calculate the standard intervals automatically. At each timepoint, 3 consecutive ECGs will be performed at approximately 2 minutes apart to determine the mean QTc interval. See the Schedule of Activities ([Table 1](#)).

When coinciding with blood sample draws for PK, the ECG assessment should be performed prior to blood sample collection such that the blood sample is collected at the nominal time.

If the mean QTc is prolonged (> 500 msec [i.e., CTCAE Grade 3]), then the ECGs should be re-evaluated by a qualified person at the site for confirmation as soon as the finding is made, including verification that the machine reading is accurate. If manual reading verifies a QTc of > 500 msec, immediate correction for reversible causes (including electrolyte abnormalities,

hypoxia, and concomitant medications with the potential to prolong the QTc interval) should be performed. Study drug will be held until the QTc interval decreases to ≤ 500 msec. Subjects will then re-start the study drug if no other cause for QTc prolongation is found or is considered drug-related resume treatment at 1 dose level lower ([Table 4](#)). If the QTc interval has still not decreased to < 500 msec after 2 weeks, or if at any time a subject has a QTc interval > 515 msec or becomes symptomatic, the subject will be removed from the study. Additional triplicate ECGs may be performed as clinically indicated.

Prior to concluding that an episode of prolongation of the QTc interval is due to study drug, thorough consideration should be given to potential precipitating factors (e.g., change in subject clinical condition, effect of concurrent medication, electrolyte disturbance) including possible evaluation by a specialist. If subject experiences a cardiac or neurologic AE (specifically syncope, dizziness, seizures, or stroke), an ECG (triplicate) should be obtained at the time of the event.

Additional ECG timepoints may be included based on the emerging data. Interpretation of the tracing will be made by a central ECG laboratory. Each ECG tracing should be labeled with the study number, subject initials, subject number, and date, and kept in the source documents at the study site. Only clinically significant abnormalities will be recorded in the AE CRF page. Clinically significant abnormalities at Screening/baseline should be recorded on the relevant medical history/current medical conditions CRF page and must be discussed with the Sponsor's Medical Monitor before enrolling the subject in the study.

